9.9.4 Safety Analysis Set

All the deviations must be justified with statistical or scientific evidence and any change to the original statistical plan must be reported, in the master file of the study and in the statistical pharmacokinetic report and final report of the study

Subject data will not be replaced, any data missing will be considered as a non-existing data and likewise data cannot be eliminated from the statistical analysis, except in the following cases:

Research subjects with pre-dose plasma concentrations in the biological matrix.

If the pre-dose concentration is lower than 5% of the C_{max} value in a subject, the subject's data can be included without adjustment in all measurements and pharmacokinetic calculations. In the cases where the pre-dose value is greater than 5% of C_{max}, the research subject must be eliminated from all study evaluations.

Data elimination due to vomiting or diarrhea

Data from research subjects who experimented vomiting or diarrhea during the course of a clinical study for immediate release products can be eliminated from the statistical analysis if the vomiting or diarrhea occurred before 2 times the median of T_{max} or 2 times the value of T_{max} obtained in the research subject during a given period.

A research subject with very low plasma concentrations for study drugs

As established by the Mexican Official STANDARD NOM-177-SSA1-2013, also research subjects that in a crossover design do not provide assessable data, both from test drug and reference drug, should not be included in the statistical analysis.

A research subject is considered to have very low concentrations if the AUC is lower than 5% of the geometrical mean of the reference medication AUC (must be calculated without inclusion of data of the research subject with atypical values).

Data exclusion due to this reason will only be accepted under scientific justification and previous review of the case by the Federal Commission for the Protection against Sanitary Risks (Comisión Federal para la Protección contra Riesgos Sanitarios, COFEPRIS).

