7.3.3 Criteria for Randomization

Eligible subjects will be rechecked at the time of admission to the study center (Day -1).

Results of the procedures performed on Day -1 as detailed Section 9.1.1, must be available prior to randomization. All inclusion and exclusion criteria will undergo a final verification before randomization.

7.3.4 Criteria for Subject Withdrawal from trial:

Subjects can be withdrawn from the study, as per the Principal Investigator's judgment, for the following reasons:

In case continuous participation in the trial is detrimental for subject's health, as per Investigator's judgment.

1. Hypertension signs and symptoms which require pharmacological treatment.
2. Syncope or shock.
3. Severe adverse reaction.
4. Serious Adverse Event.
5. Concurrent diseases or concomitant treatments not allowed by the protocol.
6. Lack of discipline.
7. Lack of compliance with the diet.
8. Lost of two samples within absorption period or near to the C_{max} .
9. If vomit occurs within therapeutic dosing interval, research subject should be withdrawn from the study and removed from the statistical analysis.

10. If any of the participant subject, during wash-out period, takes alcoholic beverages, smokes tobacco, has xanthenes containing beverages or food (coffee, tea, cacao, chocolate, mate, coke drinks, etc.) grapefruit, grapes or citrus, or grilled food (charcoal) within 24 h prior to the recruitment in the admission phase, or using any drug known by affecting the study.
11. Subjects with positive results to the drugs screening such as: amphetamines, benzodiazepines, cocaine, metamphetamines, morphine and tetrahydrocannabinoids.
12. Positive pregnancy test (qualitative or quantitative) following the study drug dosing.
13. All cases where the Principal Investigator judges as lack of compliance to the protocol or which may risk final results.

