9.9.3 PK Analysis Set

The PK Analysis Set will include all subjects who have completed the trial with adequate trial medication compliance, without any relevant protocol violations with respect to factors likely to affect the comparability of PK results, and with sufficient evaluable data to determine primary endpoints (AUC_{0-t}, AUC_{0-∞} and C_{max}) for both analytes. If subjects received concomitant medication for the treatment of an AE, their inclusion in the PK population needs to be discussed on a case-by-case basis.

All PK analyses will be based on this Analysis Set.

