9.11 Extreme Values

According to the Mexican Official Standard, NOM-177-SSA1-2013, there are several statistical tests to identify extreme values. Most of them start by calculating the student residual absolute value. Likewise, it is stated that «since studies are generally crossed designed, the most important extreme values is the extreme value for the subject». An adequate method for estimating extreme values allows to increase reliability of the study conclusion. An analysis to identify outliers (extreme) values based on the student residual estimation among subjects will be performed according to lineal mixed model in Excel.

Criterion: extreme values are those data which degree is higher than ± 2 standardized residuals intra-subject.

10 Ethical and Regulatory Issues

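### The vomiting data-exclusion rules in Protocol 7.3.4 and 9.9.4 (with the SAP) are not reconciled, and no exclusion rule for diarrhoea applies to these modified-release tablets

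*Protocol*

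**What the plan says.** - **Protocol 9.9.4** is headed as the safety set but holds the rules for removing PK data. It closes the list of exclusions: "likewise data cannot be eliminated from the statistical analysis, except in the following cases". The vomiting and diarrhoea entry covers studies "for immediate release products can be eliminated from the statistical analysis if the vomiting or diarrhea occurred before 2 times the median" Tmax, or twice the subject's own Tmax. Other entries cover pre-dose concentrations above 5% of Cmax, AUC below 5% of the reference geometric mean (after review by the authority), and crossover subjects without usable data: "research subjects that in a crossover design do not provide assessable data, both from test drug and reference drug, should not be included".
- **SAP 10.1 and 12.2** repeat the clause with the same restriction to immediate release. The protocol joins the two events with *or*, the SAP with *and*.
- **Protocol 7.3.4, item 9**: "If vomit occurs within therapeutic dosing interval, research subject should be withdrawn from the study and removed from the statistical analysis". The lead-in to that list ("Subjects can be withdrawn from the study, as per the Principal") is discretionary and leaves the decision to the investigator.
- **Protocol 9.9.3** takes completers only: "The PK Analysis Set will include all subjects who have completed the trial with adequate trial medication compliance". A second condition is that they be "without any relevant protocol violations with respect to factors likely to affect the comparability of PK results"; a third is that their data suffice. Subjects given medication for an adverse event are discussed case by case. Neither vomiting nor diarrhoea is named.
- **Products** (Protocol 1, 8.1, 8.2, 8.6): metformin XR, gliclazide MR and a modified-release combination of the two.

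**The concern.** A clause confined to immediate-release products does not reach a trial of XR and MR tablets. Because the list in 9.9.4 is closed, a literal reader would keep a modified-release profile damaged by vomiting unless it met another entry, such as the 5% AUC limit. A reader of 7.3.4 item 9 would remove the same profile. For diarrhoea, no passage that applies to these tablets gives an instruction.

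Different readings put different data behind the same 90% confidence intervals, and the error can run either way. A kept test profile with lost exposure pulls the ratio down and costs power. A kept reference profile pushes the ratio up and can help a product whose true ratio is 0.80 to pass. The trial is open-label, so an exclusion decided after assay would be decided with treatment and concentrations both known. Protocol 3.1.8 and 4 list vomiting and diarrhoea among very common gastrointestinal reactions (at least 1 in 10). That is a general frequency class, not a single-dose rate.

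**Working it through.** **1. The passages side by side**

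| Question | 7.3.4 item 9 | 9.9.4 | SAP 10.1, 12.2 | 9.9.3 |
|---|---|---|---|---|
| Event | vomiting | vomiting or diarrhoea | vomiting and diarrhoea | not named |
| Release type | no limit | immediate release | immediate release | no limit |
| Window | dosing interval, undefined | 2 × Tmax | 2 × Tmax | none |
| Force | should, under a discretionary lead-in | optional | optional | general filter |

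Item 9 is not carried into 9.9.3, 9.9.4 or the SAP. The 5% AUC entry does not fill the gap: an average profile that loses 80% still has about 20% of the reference mean.

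**2. The plan's own sample size**

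Inputs (Protocol 9.7, SAP 7): CV 23%, ratio 0.95, one-sided alpha 0.05, power 90%, 32 evaluable, 40 randomized.
- Within-subject SD on the log scale: √ln(1 + 0.23²) = 0.227.
- The printed formula, with this SD and n read as per sequence, needs 15.8, so 16 per sequence and 32 in total. Entering 0.23 directly needs 16.1, so 17 and 34.
- TOST power at 32 subjects is 90.4%. 32/(1 − 0.20) = 40. The plan's figures reproduce.

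**3. One affected profile kept**

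Model: paired log-differences with SD 0.227 × √2 = 0.321, 32 subjects, 90% CI required within 0.80–1.25, one endpoint, 400,000 simulations per cell. One profile is multiplied by 0.8, 0.5 or 0.2. The documents give no exposure loss, so these are assumptions. The mean log-difference moves by ln(factor)/32. At 50% loss in the test period, for example, 0.95 × exp(ln 0.5/32) = 0.930. The residual variance rises as well.

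| Case | 20% loss | 50% loss | 80% loss | Comparison |
|---|---|---|---|---|
| Test kept, power at 0.95 | 88.1% | 79.5% | 45.7% | 89.6% if removed (n = 31) |
| Reference kept, power at 0.95 | 92.1% | 93.6% | 89.7% | 89.6% if removed |
| Reference kept, type I error at 0.80 | 6.2% | 8.3% | 9.3% | 5% |

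**4. Sensitivity to the model**

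The documents do not say which treatments enter the step 1 model. If residual error is pooled over the three metformin treatments (subject and treatment effects), test-kept power becomes 89, 81 and 53%, and reference-kept type I error 6, 9 and 13%.

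**5. More than one endpoint at the margin**

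Step 1 needs all six intervals to pass. Suppose two metformin endpoints both sit at 0.80 and the same reference profile is affected in both. In the paired model the joint error is about 1.6, 2.4 and 2.9% at an assumed correlation of 0.5, and 4.0, 5.6 and 6.4% at 0.9.

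**6. How often an event might occur**

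Step 1 compares two metformin-containing treatments: 40 × 2 = 80 doses. At assumed rates of 0.5, 1 and 2% per dose, 1 − (1 − r)^80 = 33, 55 and 80% for at least one event. This counts every event, including those that item 9 would remove and those with no exposure loss. It is not the chance that an interval changes.

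**The case against.** The strongest reply is that vomiting is already covered. Item 9 of 7.3.4 has no limit on release type and orders removal from the analysis as well as withdrawal. A reader might infer that 9.9.4 holds the only such rule and that vomiters therefore stay in; item 9 contradicts that. A reader might also infer that vomiting in period 4 escapes because no later dose remains to be withheld, but removal from the analysis still applies there. Subjects actually withdrawn are settled too, since 9.9.3 takes completers only. All of this stands. What stays open is the undefined interval, the discretionary lead-in, the conflict with the closed list in 9.9.4, and diarrhoea.

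A second tempting criticism is that twice Tmax names no analyte and, if taken from study data, is known only after assay. On the protocol's background figures it would be 14 h for metformin (2 × 7 h, from a 500 mg XR tablet) and 12–24 h for gliclazide (2 × the 6–12 h plateau). This matters only if the immediate-release clause is stretched to these tablets; read as written, it does not apply to them.

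Third, 9.9.3 already filters on comparability, and the residual screen in 9.11 would flag many large losses. But 9.9.3 names neither event, and 9.11 only defines a flag ("extreme values are those data which degree is higher than" ±2 standardized residuals) without saying what follows from it.

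Finally, the plan follows NOM-177-SSA1-2013, which was not available here. Whether that standard deals with modified-release products is unknown, so any new wording must be checked against it.

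**Conclusion.** The point holds as an inconsistency: two vomiting rules that can give opposite answers for the same profile, and no applicable rule for diarrhoea. It should be corrected.

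Its size depends on an assumed exposure loss. At 20% the effect is small: about 2 points of power, or 1 point of type I error. At 50–80% a single kept test profile takes power from about 90% to between 80 and 46%, and a kept reference profile takes single-endpoint type I error to 8–9% (9–13% with pooled residual error).

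A reader might take 9% as the trial's false-positive rate for bioequivalence. The documents do not support that, because all six intervals must pass and the joint error is lower when several endpoints sit at the margin. Nor do they show that any such event occurred or changed a result.

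**What to change.** In Protocol 9.9.4, SAP 10.1 and SAP 12.2, replace the immediate-release clause with one data-exclusion rule that applies to these modified-release tablets and agrees with 9.9.3 and with the data-removal part of 7.3.4 item 9. It should state:

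1. which event or events count, in the same words in both documents;
2. a post-dose window set without study concentrations;
3. whether the affected period or the whole subject is removed.

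Fix the exclusion list before concentrations are released, and report the 90% confidence intervals with the affected data included and excluded. SAP 12.1 and 15.2 already carry statements about results. If concentrations are known, report the intervals under each reading instead. Check the wording against NOM-177-SSA1-2013.

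On withdrawal from dosing, item 9 and the lead-in of 7.3.4 must be reconciled; no clinical rule is proposed here.

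The cost is wording changes in two documents and one sensitivity run. A window set in advance may misclassify a few events near its edge; the with-and-without intervals would show whether that matters.

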9.10 Statistical Analyses Description

9.10.1 General Considerations

Statistical analysis and analysis of PK parameters will be performed using Phoenix WinNonlin software Version 6.3 (PPD [REDACTED]).

Descriptive statistical methods will be used to summarize demographic characteristics, pharmacokinetics parameters and adverse events. After the data base closing

Individual plasma concentration-time will be tabulated and plotted. Primary pharmacokinetics parameters, AUC and C_{max} , will be tabulated and plotted by subject. Likewise, differences and odd ratios for test/reference will be tabulated for each subject for those parameters. Plasma concentration - time graphs will be made using arithmetic and semi-logarithmic scale. All de calculations will be determinated in concordance with NOM-177-SSA1-2013

A complete description of the analyses will be given in the statistical analysis plan (SAP) into the protocol.

Statistical Analysis

9.10.2 Analysis of primary and secondary endpoints

The following sequential testing of a priori ordered hypotheses will be applied, as shown below. Bioequivalence test methodology will be used in all 3 steps:

1. Test bioequivalence of fixed combination and separate tablets
2. Test absence of an effect of Gliclazide on the PK of Metformin
3. Test absence of an effect of Metformin on the PK of Gliclazide

Bioequivalence in step1:

A mixed model will be applied to log-transformed C_{max} , AUC_{0-t} and $AUC_{0-\infty}$ (both analytes) with treatment, period and sequence as fixed effects, and subject (sequence) as a random effect. Based on the residual error term 90% confidence intervals will be computed for the estimated differences Test – Reference, resulting in 90% confidence intervals for the Test/Reference ratios after back-transformation.

Drug-drug interaction in steps 2 and 3:

A mixed model will be applied to log-transformed C_{max} , AUC_{0-t} and $AUC_{0-\infty}$ (one analyte) with treatment as fixed effect, and subject as a random effect. Based on the residual error term 90% confidence intervals will be computed for the estimated differences Test – Reference, resulting in 90% confidence intervals for the Test/Reference ratios after back-transformation.

1. Bioequivalence will be concluded, if all six 90% CIs for all six primary endpoints reside within the acceptance range [0.80 – 1.25]
2. Absence of an effect of Gliclazide on the PK of Metformin will be concluded, if all three 90% CIs for Metformin endpoints reside within the range [0.80 – 1.25]
3. Absence of an effect of Metformin on the PK of Gliclazide will be concluded, if all three 90% CIs for Gliclazide endpoints reside within the range [0.80 – 1.25]

Additionally, the primary endpoints will be descriptively analyzed and graphical displays (Box-whiskers-plots) will be prepared.

Statistical model in the variance analysis of mixed effects should be applied for log-transformed parameters C_{max} , AUC_{0-t} and $AUC_{0-\infty}$ (one analyte) with TREATMENT as fixed effect and SUBJECT as randomized effect. Based on residual errors, confidence interval of 90 % will be built for estimated differences for test - reference, resulting in a confidence interval of 90 % for the test/reference ratio following transformation.

Using minimum mean squares for AUC and C_{max} , two-side t test will be performed (Schuirmann's test) by constructing confidence intervals of 90 % for test/reference ratios. If and only if intervals are within interval (80, 125), bioequivalence will be proven for both drugs.

Bioequivalence is concluded if 6 confidence intervals for the analytes are included into the bioequivalence limits.

8.11.4 Analysis of secondary endpoints

All other PK endpoints will be analyzed using descriptive methods. Graphical displays will be also prepared where appropriate.

9.10.3 Safety Analyses

All safety endpoints will be analyzed descriptively.

Vital signs measurements and ECG recordings will be individually listed by subject number, treatment and time point and flagged according to reference ranges. All variables will be presented by descriptive statistics by treatment and time point for the values obtained during the treatment periods and overall and by treatment sequence at screening and the end of study visit.

All hematology and biochemistry parameters, including hematoglucoest (HGT) results, will be listed and summarized using descriptive statistics on observed values by treatment and time point for the values obtained during the treatment periods and overall and by treatment sequence at screening and end of study visit. Urinalysis will be summarized in frequency tables.

In addition, shift tables for laboratory tests based on a classification of values as low, normal, or high with respect to the reference range could be summarized and presented by time point.

After coding of AEs according to the Medical Dictionary for Regulatory Activities (MedDRA) classification (current version) and assignment to a system organ class (SOC), all AEs recorded during the course of the trial will be listed by treatment and subject number and tabulated by MedDRA SOC and Preferred Term (PT).

The frequency of treatment-emergent AEs (TEAEs) will be summarized using the frequency of events and the number of subjects experiencing these events per treatment, PT, and SOC.

In addition, all TEAEs will be tabulated by intensity and relationship to drug per treatment.

An AE will be tabulated by intensity since the first investigational product administration of each period or if it occurred before administration and worsened during the period. The results will be presented as a frequency proportions or histograms.

9.10.4 Analysis of Further Endpoints

Individual concentrations of Metformin and Gliclazide in plasma will be listed and summarized by treatment. Individual plasma concentration-time profiles (linear and semi-logarithmic scales) will be plotted by treatment (showing all subjects simultaneously) and by subject (showing all treatments for a subject). Mean plasma concentrations will be plotted by treatment with SD using scheduled time points (linear and semi-logarithmic scales).

Demographic parameters (such as ethnic group, sex, age, height, weight, BMI) and other baseline characteristics (such as smoking history, diet, previous medications taken prior to screening visit, nicotine consumption, alcohol consumption, intake of caffeine or xanthine containing beverages) will be summarized by means of tabulated descriptive statistics for all subjects overall and by treatment sequence.

9.11 Extreme Values

According to the Mexican Official Standard, NOM-177-SSA1-2013, there are several statistical tests to identify extreme values. Most of them start by calculating the student residual absolute value. Likewise, it is stated that «since studies are generally crossed designed, the most important extreme values is the extreme value for the subject». An adequate method for estimating extreme values allows to increase reliability of the study conclusion. An analysis to identify outliers (extreme) values based on the student residual estimation among subjects will be performed according to lineal mixed model in Excel.

Criterion: extreme values are those data which degree is higher than ± 2 standardized residuals intra-subject.

10 Ethical and Regulatory Issues

10.1 Principal Investigator's Responsibilities

The Principal Investigator is responsible for the study conduct at the site. He/she will make sure that the study is conducted according to the clinical protocol, ethical principles established in the Declaration of Helsinki, ICH, GCP and established regulation NOM-177-SSA1-2012, which states tests and procedures to show that a drug is interchangeable as well as the requirements which Authorized Third-Parties should fulfill to perform the tests. The Investigator should ensure that only subjects who have provided their informed consent are included in the study.

10.2 Information for the Subject and Informed Consent

An additional requirement for each subject before their participation in the study, is to have a written informed consent, which should be given before any study-related activity is carried out.

Therefore, the Principal Investigator or designated personnel should provide appropriate information before obtaining informed consent.

Subject's Information Sheet should be elaborated in Spanish, according to the ICH GCP and will be provided by the Sponsor with the purpose to get informed consent. Besides providing written information to the potential subject, Investigator or designated person will inform them verbally all relevant aspects of the study, using language chosen so that information can be fully and easily understood by the subjects. Subject will be given enough time to read the information and ask questions and request additional information and explanations.

After providing information to the subject, informed consent form should be signed and dated by the subject, the Principal Investigator and two witnesses.

The dated and signed informed consent will be kept in the study site and should be securely filed so that files can be retrieved at any moment for monitoring, auditing and inspection purposes. A copy of the signed and dated informed consent form should be provided to the subject before their participation in the study.

Whenever new relevant information arises for the informed consent, the Investigator will revise subject's information and any other written information to be provided to the subjects which should be submitted to the Committees for review and approval.

Revised and approved version of the written information will be used. The Principal Investigator or designated personnel will explain each subject all changes made to the previous version and will obtain a new written consent to continue his participation in the study. Subject will be given enough time to read the information and ask questions, and request additional information and explanations about changes.

